The aim of this study was to evaluate the effect of the application of a protocol of the neural mobilization in individuals with chronic low back pain with or without irradiation for lower limbs, isolated or associated with drug treatment. In addition, to evaluate the effect of the technique on the pain intensity and the functional capacity of the volunteers.

MATERIALS AND METHODS:

This was a prospective randomized, controlled, parallel-group trial. All the study procedures were conducted in accordance with Research Ethics Committee with Human Beings of the Biomedical Sciences Institute of the University of São Paulo – São Paulo,

Brazil (CAAE: 56978016.1.0000.5467). The trial was also registered in Clinical Trials (clinicaltrials.gov - NCT02671409).

The participants were recruited for evaluation by establishing the inclusion and exclusion criteria of the study. Were included in the study individuals of both genders who corresponded to the following criteria: with chronic low back pain, irradiated or not to one of the lower limbs; age from 18 years; score ≥ 4 on the analogue pain scale (VAS).

Were excluded of the study individuals with acute low back pain; spondylolisthesis or fibromyalgia; previous spinal surgery; any sequelae that causes limitation in the range of motion of the lower limb or joint deformity; that present caution for neural mobilization such as: metal plates, screws, neurological disorders; cancer; cognitive disturbances or apparent impossibility; any type of pain in other regions that is not characteristic of low back pain; advanced diabetes mellitus; patients under physiotherapeutic treatment for the same reason; decompensated cardiovascular diseases; significant changes in sensitivity; edema in lower limbs and pregnant women.

After eligibility, all the procedures to be performed during the study were elucidated, and the subjects signed the Free and Informed Consent Term, according to Resolution 466/12 of the National Health Council - Brazil, confirming their participation in the research.

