Thirty-five individuals volunteers participated in this study, with a mean age of 49.64 years, were 21 women and 14 men. After being selected, the volunteers were allocated to three groups: Neural Mobilization Group (MOB), consisting of individuals with low back pain and treated with the technique, with a total of 18 participants; Neural Mobilization + Medication Group (MOB + MED), constituted by individuals with low back pain, who underwent the mobilization technique associated with medication, a total of 12 participants; and the control group (CONTROL) constituted by healthy individuals without any kind of injury or pain complaint who received the application of the neural mobilization technique, with a total number of 5 participants.

After fulfilling the eligibility criteria, a clinical evaluation and assessments of pain and mobility were carried out, and a quality of life questionnaire was applied (details below).

In order to preserve the accuracy of the intervention effectiveness, participants who missed more than two sessions were excluded from the study. All subjects were assessed by a blinded evaluator. Both participants and evaluator were encouraged not to discuss the received intervention.

First, all personal data from each subject were obtained. Age, body mass, height, profession, school education. After this first step, the participants were submitted to two evaluations, prior to and at the end of the therapeutic program. Both to assess the pain

intensity and to assess the mobility of the lumbar spine, as well as the application of a quality of life questionnaire. A follow up was done thirty days after the end of the treatment to verify the effect of the protocol after the patients return to the normal daily life activity. A characterization and physical examination card were used for a better analysis of the volunteers. The subjects in all three groups were submitted to the same evaluation protocol.

A visual analogue scale (VAS) was used for the assessment of pain intensity, which consists of a line ranging from 0 to 10, where zero characterizes absence of pain and ten, worst pain. After clarifying how to complete the scale, the volunteer was asked to mark a point on the line that indicated the intensity of pain that he or she was feeling at moment of the evaluation [9].

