Regarding the Roland-Morris Disability Questionnaire (RMDQ) and Oswestry Disability Index (ODI), we also used to analyze the level of physical disability induced by low back pain in each study volunteer. In our work, we can suggest that the protocol proposed was able to improve the disability of individuals treated only with the neural mobilization technique from mild to normal in almost all patients in RMDQ. It should be mentioned that the individuals treated with the combination of medicaments had a higher level of disability than the patients that received only MOB treatment in RMDQ.

In RMDQ, the results obtained so far in this questionnaire suggest that the protocol proposed in this study was able to aid in the improvement of the mild and moderate disability of individuals treated only with the neural mobilization technique and also associated with drug treatment. It should be mentioned that the individuals treated with the combination of treatments (MOB + MED group) had a higher level of disability than the MOB group.

We could also observe an improvement in the individuals' disability through ODI, comparing before and after the technique, where the subjects treated with MOB only had a lower level of disability compared to the MOB + MED group, both of which obtained a reduction of the level of disability after the application of the proposed protocol.

Based on both questionnaire applied in this study, we could demonstrate their success in improving the quality of life from all patients analyzed in this program.

This technique proves to be a possible adjunct therapy to the drug treatment, since it has no side effects, and may help in reducing the dose and administration period of the medication. In addition to improving their functional capacity and quality of life, thus demonstrating their importance for clinical practice.

CONCLUSION:

In summary, we can affirm that the technique chosen for the treatment of individuals with chronic low back pain, with or without irradiation to one of the lower limbs, was effective in reducing the pain intensity of these patients when comparing the initial with the final evaluation, as well as between treatment sessions.

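### The three-group study is labelled randomized and controlled, but its control group is healthy people outside the inclusion criteria, and how patients came to be with or without medication is not stated

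*Combined protocol and SAP*

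**What the plan says.** All references are to the combined protocol and SAP unless stated otherwise.

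- **Design label** (MATERIALS AND METHODS): "This was a prospective randomized, controlled, parallel-group trial". Neither document mentions randomization anywhere else. The separate Protocol describes a single treated group.
- **Aim** (end of the INTRODUCTION): to study the technique in chronic low back pain, "isolated or associated with drug treatment".
- **Inclusion** (MATERIALS AND METHODS): people "with chronic low back pain, irradiated or not to one of the lower limbs", aged 18 or over, with a "score ≥ 4 on the analogue pain scale (VAS"). No separate criteria are printed for healthy volunteers.
- **Group formation**: "After being selected, the volunteers were allocated to three groups". MOB is described as "consisting of individuals with low back pain and treated with the technique, with a total of 18 participants". MOB + MED is 12 people with low back pain who had the technique together with medication. The third is "the control group (CONTROL) constituted by healthy individuals without any kind of injury or pain complaint", five people who also received the technique.
- **Analysis**: repeated-measures ANOVA with Tukey-Kramer comparisons for between-group differences and paired t-tests within groups. No baseline adjustment is stated.
- **Use made of the comparison** (RESULTS, Visual Analogue Scale): the absence of a significant MOB versus MOB + MED difference is taken to suggest that the technique alone can improve pain.
- **Disclosure** (DISCUSSION): "individuals treated with the combination of medicaments had a higher level of disability than the patients that received only MOB treatment in RMDQ".

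**The concern.** A randomized, controlled label tells the reader that group membership was decided by chance and that the control group shows what happens to comparable patients without the treatment. The group definitions do not deliver the second for any group. They contradict the first for CONTROL and leave it undocumented for the two patient groups.

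What is at stake is the meaning of every between-group statement. Under this label, the thirty-day VAS values of 1.5 (MOB) and 2.6 (MOB + MED), and the conclusion drawn from the non-significant difference between those groups, read as an unconfounded comparison of the technique with and without medication. If patients were grouped by the medication they already took, severity and the reasons for taking it are mixed into that comparison.

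**Working it through.** The plan gives no figure to reproduce here. The check sets the passages side by side and then examines the baseline counts.

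**Step 1: CONTROL against the inclusion criteria**

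| Requirement | CONTROL as described |
|---|---|
| Chronic low back pain | Healthy, no injury or pain complaint |
| VAS at least 4 | VAS zero until follow-up (RESULTS, Visual Analogue Scale) |

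All five fail both criteria, so they cannot have been drawn by chance from the eligible pool. CONTROL also received the technique, so the number of groups with pain and without the technique is zero. Its VAS stays at zero and all five are in the best RMDQ and ODI bands (Tables 2 and 3). It therefore cannot show pain relief. None of this needs a statistical test.

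**Step 2: how patients entered MOB or MOB + MED**

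The text says only that volunteers were allocated. It gives no sequence, ratio, concealment or rule for who had medication. RESULTS and DISCUSSION speak of medication as something the patients were using or taking, which fits existing use but does not state it.

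**Step 3: baseline of the two patient groups**

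Counts come from Tables 1 to 3 and the RMDQ text in RESULTS. The test is Fisher's exact test, two-sided.

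| Baseline item | MOB | MOB + MED | p |
|---|---|---|---|
| Working full or part time | (10 + 7)/18 = 17/18 | (1 + 3)/12 = 4/12 | 0.0006 |
| Unemployed or disabled | 0/18 | (3 + 3)/12 = 6/12 | 0.0016 |
| ODI 0-20% | 7/16 | 0/11 | 0.022 |
| RMDQ 0-10 | 15/17 | 6/11 | 0.076 |
| Male | 7/18 | 5/12 | 1.0 |
| Severe RMDQ | 2/17 | 2/11 | 1.0 |
| ODI above 40% | 2/16 | 3/11 | 0.37 |

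Mean age is 43.4 versus 43.3 years. Multiplying the first four p-values by four (Bonferroni) gives about 0.003, 0.006, 0.09 and 0.31, so only the work-status differences survive. The two work-status rows use overlapping categories and are not independent evidence. Mean initial finger-to-floor distance is 20.66 cm versus 25.5 cm (RESULTS, Lumbar mobility), with no SD given.

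**Step 4: sensitivity to missing questionnaires**

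ODI is missing for 18 − 16 = 2 MOB patients and 12 − 11 = 1 MOB + MED patient. If both missing MOB patients were above 20% and the missing MOB + MED patient was in 0-20%, the split becomes 7/18 versus 1/12, p = 0.10. The ODI difference is not robust to this.

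**Step 5: what a non-significant difference can carry**

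Take a two-sided 5% level (the document does not state sidedness) and a simple comparison of two means. The standardized difference detectable with 80% power is (1.960 + 0.842) × √(1/18 + 1/12) = 2.802 × 0.3727 = 1.04 SD. Power is 27% for 0.5 SD and 57% for 0.8 SD. Non-significance at this size is not evidence of similarity, even with comparable groups.

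**The case against.** The strongest reply concerns the two patient groups. The document says the trial was randomized and that volunteers were allocated, and nowhere says that medication was already in use. The participant flowchart (Figure 2) is not visible in the copy reviewed and may describe assignment. The counts are completers: 60 were screened, 35 finished, and anyone missing more than two sessions was excluded. Uneven exclusion could produce unequal sizes and imbalance after a proper randomization. The tests are post hoc and small, and several characteristics are balanced. Baseline VAS for MOB + MED is not in the readable text. All of this stands. A reader might infer that MOB versus MOB + MED was certainly not randomized, or that the 18/12/5 sizes prove it. The documents do not support either reading.

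A reader might also infer that CONTROL could not change on any measure. That goes too far. VAS can rise from zero, so CONTROL can register provoked pain. Tables 2 and 3 report bands rather than scores, and finger-to-floor distance is not reported to be at a limit.

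Finally, the stated aim need not be read as estimating the effect of adding medication, the 25% and 28% mobility gains are within-group results, and the DISCUSSION discloses the disability difference. This limits the damage but does not remove it, because RESULTS does draw an inference from the between-group comparison on pain. Nothing in the reply rescues the label for CONTROL.

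**Conclusion.** The point holds, with different certainty for its two parts.

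- **CONTROL: established from the text.** The group is defined by health, fails the printed criteria and received the technique. As a description of the three-group study, randomized and controlled is wrong as written.
- **MOB versus MOB + MED: suggestive, not proven.** The wording on medication, the document's own remark on disability and the work-status imbalance (17/18 versus 4/12; 0/18 versus 6/12) point to cohorts defined by medication use. ODI is weaker evidence, and RMDQ does not reach the document's 5% level. Randomization of the 30 patients cannot be excluded.

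This rests on the tabulated completer counts and on the readable text, without the flowchart. The label must be corrected because it determines what the between-group analysis can support. Within-group before/after results do not depend on group comparability and are not affected by this point.

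**What to change.** 1. Remove randomized and controlled as a description of the three-group study. Present CONTROL as a healthy reference group exempt from the pain criteria, take it out of efficacy contrasts, and keep it only to describe tolerance or provoked pain.
2. State how patients entered MOB or MOB + MED. If they were randomized, describe the procedure and limit the word to that comparison. If not, call the study a non-randomized before/after study in two patient cohorts with a healthy reference group.
3. Unless randomization is documented, label MOB versus MOB + MED comparisons as non-randomized, show baseline ODI, RMDQ and work status beside them, word the drug-treatment aim as change within each cohort, and withdraw the inference in RESULTS from the non-significant difference.

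The cost is rewording plus baseline values that are already tabulated; no new data are needed. The downside is a weaker design label.

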The Neural Mobilization technique was performed by the same physiotherapist, from the first to the last session, on interleaved days. The protocol of the technique consists in applying a total number of 10 interventions in each patient, with a total duration of 10 minutes, divided into four series of 2 minutes with a 30-second interval between each series according to the protocol proposed in 2012 by Santos et al [15].

The technique was applied with the participant seated in a suitable chair, with a flexed hip (90) and extended knees (figure 1). Next, the physiotherapist applies the technique only to the lower limb in which the individual presents some impairment due to low back pain, observed in the previous physical examination, or in case of absence of irradiation for any of the limbs, the technique was applied only to the right lower limb according to Santos et al 2012 [15].

In the period from July 2016 until September 2017, we screened 60 subjects for eligibility but only 35 individuals had finished all the study protocol according to the includes and exclude criteria. Next, in figure 2 we have a flowchart about the study design, that explain all the procedures realized with the volunteers in all groups.

The statistical analysis was the ANOVA test with repeated measures for the time factor were performed to test between-group differences (followed by the Tukey-Kramer post hoc test), and a paired t test was performed to test within-group differences. The level of significance for the statistical analysis was 5% ($p \le 0.05$), using the standard error as mean \pm SEM [16].

RESULTS:

A total of 35 patients concluded the study and were analyzed. Characteristics of participants included in each group were presented in Table 1 and were homogenous for age at baseline. After the application of the Neural Mobilization technique, the patients were reassessed and the data obtained in both, the initial and final evaluation were submitted to statistical analysis.

Visual Analogue Scale:

Our results demonstrated an improvement in pain in patients treated with neural mobilization. There was a mean reduction in the VAS scale from average 8.47 to 4.05, which was statistically significant in group MOB (Figure 3).

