The decrease of pain sensitivity started at the 4th session for patients treated with neural mobilization only (MOB) and from the 5th treatment session for the patients using medicament plus therapeutic treatment group (MOB + MED). The improvements remained until the end of the treatment (Figure 3).

EVA was 1.5 for MOB group and 2.6 for MOB+MED thirty days after the end of the sessions. Control group (CONTROL), composed of individuals without any kind of pain or injury and who were treated with the neural mobilization technique, it was noted pain intensity on the VAS scale remained at zero until the follow up evaluation (Figure 3).

It should be mentioned that it was not possible to observe a statistically significant difference between the MOB and MOB + MED groups, which suggests that the Neural Mobilization technique alone can improve the pain of these individuals, and it could be considered an adjuvant therapy to the drug treatment of patients (Figure 3).

Roland-Morris Disability Questionnaire (RMDQ):

By adding the yes answers and reaching a value equal to or lower than 10 points, it shows that the person with low back pain presents without some kind of disability, that is, despite the pain, there is no impeding the accomplishment of their daily life tasks. However, if the total varies between 11 and 14 yes / indicated alternatives, it indicates a mild or moderate inability of this individual to perform their daily activities. When the positive responses are equal to or greater than 15, it indicates that this individual has a severe disability [12].

In the MOB group, 17 individuals were evaluated. In the initial measurement, we observed that 15 individuals presented in the normal parameter, not showing any kind of incapacity in performing daily life activities. Two individuals from the same group, presented, in the initial measurement, a severe incapacity to perform the activities of daily living. At the end of the treatment, this questionnaire was reapplied, and 16 of the subjects presented normal parameters, and one of the individuals with severe disability returned to normal levels; the other individual who also presented a severe level of disability, partially reversed their condition, going to mild/moderate disability when performing activities of daily living (Table 2).

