The mobility of lumbar spine was evaluated and subjects with low back pain and treated with Neural Mobilization (MOB), had at the initial evaluation (I) an average of 20.66 cm from the ground and of 15.4 cm at the final evaluation, an improvement of 25% (* p <0.0001). Patients with LBP treated with medication and neural mobilization treatment (MOB + MED), presented and initial distance (I) of 25.5 cm (average) from the ground and of 18 cm (F) at the end of treatment. There was an improvement of 28 % of the recovery, a statistically significant improvement (#p<0.05) compared with the same group before treatment. In Control group, no difference was observed (Figure 4).

DISCUSSION:

Low back pain represents one of the biggest health problems all over the world, which causes an effective social and economic impacts on the society, linked to the high level of disability and work absence [17] [18] [19] [20].

Some studies show that the costs associated with chronic low back pain exceed a few billion dollars [20], which shows us how important is the search for effective and low-cost treatments aimed at minimizing the global financial impacts caused by chronic low back pain.

The European guidelines for chronic low back pain recommend several types of conservative treatment for this condition, among them, manual therapies such as manipulations and mobilizations [21].

Some systematic reviews state that use manipulation and mobilization to treat chronic low back pain may have positive effects, but they emphasize that their effect may vary according to the time of application, patient and physiotherapist handling, type of technique, the range of application, and the outcomes analyzed [22] [23].

Neural mobilization is a type of mobilization, and a noninvasive physiotherapeutic technique that aims to reestablish the conductivity of the nerve impulse, reducing the intensity of pain caused by peripheral neuropathy and, in some studies with laboratory animals with neuropathic pain, has been able to regenerate the sciatic nerve after the application of the technique [24] [15].

Serrano et al, 2002, says that pain is impossible to measure directly and objectively, but that it would be possible to perform a quantitative estimation of pain intensity, with VAS (Visual Analog Scale). This is one of the best scales used to make the description of the pain more objective and accurate and was chosen for this work [9].

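### The between-group ANOVA plans no baseline adjustment and names no model term; read as the group main effect, it mixes the pre-treatment gap into MOB versus MOB + MED

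*Combined protocol and SAP*

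**What the plan says.** The statistical paragraph of Materials and Methods in the combined protocol and SAP has one between-group method: "ANOVA test with repeated measures for the time factor were performed to test between-group differences (followed by the Tukey-Kramer post hoc test". Within groups, "a paired t test was performed to test within-group differences". On the error rate: "The level of significance for the statistical analysis was 5" per cent, with sidedness not stated. No baseline covariate, change score or group-by-time term appears there or elsewhere in that document.

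The design is described so: "This was a prospective randomized, controlled, parallel-group trial". The paragraph that sets out the three groups gives no method of randomisation. It lists MOB ("treated with the technique, with a total of 18 participants"), MOB + MED with 12 participants, and 5 healthy controls.

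Under Lumbar mobility, MOB had "an average of 20.66 cm from the ground and of 15.4 cm at the final evaluation", and MOB + MED "presented and initial distance (I) of 25.5 cm (average) from the ground and of 18 cm (F) at the end of treatment". The other printed baselines also differ. On the ODI, 7 of 16 MOB patients and 0 of 11 MOB + MED patients were in the lowest disability band (Table 3). On the RMDQ, 15 of 17 and 6 of 11 were in the normal band (Results text and Table 2).

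The one reported test of MOB against MOB + MED is on the VAS: "it was not possible to observe a statistically significant difference between the MOB and MOB + MED groups". The p-values in the legends of Figures 3 and 4 all compare times within a group.

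**The concern.** One aim of the document is to study mobilisation alone and together with medication, and the ANOVA sentence is the only test planned for that comparison. In a repeated-measures ANOVA the group main effect, and Tukey-Kramer on the group means, compare averages over all times, including the value taken before any treatment. That term does not ask whether the groups responded differently. When groups start apart, as here, the starting gap is carried into the result. When an outcome has only two time points, a true difference at the end is also halved by averaging. The group-by-time term avoids both problems, but the text does not name it. As written, the plan allows either term and adjusts for baseline under neither.

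**Working it through.** **Check on the printed means.** The document gives mobility gains of 25% (MOB) and 28% (MOB + MED). From its means, 5.26/20.66 = 25.5% and 7.50/25.5 = 29.4%. The second agrees with 28% only if the final mean of 18 cm is rounded from about 18.36 cm (25.5 x 0.72). The printed 18 cm is used below and the effect of the rounding is noted. The three-group document states no sample size or power for a between-group comparison, so there is none to reproduce.

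**Finger-to-ground distance, MOB + MED minus MOB (larger is worse).**
- Initial: 25.5 - 20.66 = +4.84 cm.
- Final: 18 - 15.4 = +2.60 cm.
- Average of the two, which the group main effect estimates: (4.84 + 2.60)/2 = +3.72 cm.
- Part due to the initial gap: 2.42/3.72 = 65%.
- Improvement: 7.50 v 5.26 cm, so MOB + MED gained 2.24 cm more.

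With a final mean of 18.36 cm the average would be +3.90 cm and the extra gain 1.88 cm; the directions are the same.

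**Baseline-adjusted difference.** With equal SDs the ANCOVA slope equals the correlation rho between initial and final values, and the adjusted difference is 2.60 - rho x 4.84. The documents give neither rho nor an SD. Under assumed values:
- rho 0.3: +1.15 cm
- rho 0.5: +0.18 cm
- rho 0.6: -0.30 cm
- rho 0.7: -0.79 cm

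The direction of the adjusted difference is therefore not known from the printed data.

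**Power with two time points.** Inputs: n = 18 v 12 (document); two-sided 5%, equal SDs and a true final difference of 1 SD with no initial difference (assumed). The factor sqrt(1/18 + 1/12) is 0.3727. At rho = 0.6 the noncentrality values are:
- Group main effect: 0.5/(0.3727 x sqrt((1 + rho)/2)) = 1.50 on 28 df.
- Group-by-time: 1/(0.3727 x sqrt(2(1 - rho))) = 3.00 on 28 df.
- ANCOVA: 1/(0.3727 x sqrt(1 - rho^2)) = 3.35 on 27 df.

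Power from the noncentral t distribution:

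| rho (assumed) | Group main effect | Group-by-time | ANCOVA |
|---|---|---|---|
| 0.3 | 36% | 59% | 77% |
| 0.5 | 32% | 74% | 85% |
| 0.6 | 30% | 83% | 90% |
| 0.7 | 29% | 92% | 95% |

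The efficiency of the group main effect relative to ANCOVA is (1 - rho)/2, or 0.20 at rho = 0.6. The RMDQ and ODI were analysed in slightly fewer patients (17 v 11 and 16 v 11), which lowers every column a little.

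**VAS.** It was recorded at the start, during the sessions, at the end and at follow-up. If all 10 sessions were measured (assumed), there are 13 values and the baseline has weight 1/13. With a constant 1-SD effect after baseline, equal correlations and rho = 0.6, the noncentrality is (12/13)/(0.3727 x sqrt((1 + 12 x 0.6)/13)) = 3.12, and the group main effect has about 85% power. An effect that builds up over the sessions would lower this, but mainly because early sessions are averaged in.

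**The case against.** The strongest reply is that the sentence does not name the tested term. A group-by-time test, or Tukey comparisons at single times, would also fit it. Under group-by-time the baseline is subtracted, and the power cost against ANCOVA in the two-time-point case is modest: 83% v 90% at rho = 0.6. This stands. A reader might infer that the plan definitely tests the group main effect and so loses most of its power; the text supports only the conditional statement.

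A reader might also blame the non-significant VAS comparison on this choice. The documents do not support that: the two-time-point figures do not apply to the VAS.

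Nor do the documents report a false group difference. Mobility has only within-group p-values, and the RMDQ and ODI are given as category counts without a test. The 3.72 cm contrast is what the method would yield, not a reported result.

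Finally, if allocation was random, a chance imbalance leaves the unconditional type I error at 5%. If it was not, ANCOVA can itself be confounded by the baseline difference. Both points are correct. It would go too far to say that the groups were not randomised: the document says they were, but describes no procedure, and the baselines differ. Under either assumption, leaving the initial value unadjusted has no advantage.

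**Conclusion.** The point holds in a conditional form. The between-group test uses unadjusted values, and its model term is unspecified. If the group main effect is the term, the pre-treatment gap supplies 65% of the mobility contrast, which points against the group with the larger raw improvement. That opposition holds for raw change; for a baseline-adjusted difference the sign depends on an unknown correlation. For mobility, RMDQ and ODI, reported only at the initial and final evaluations, the group main effect would have about 29% to 36% power where ANCOVA has 77% to 95%. These ranges rest on a 1-SD final difference, equal SDs and correlations of 0.3 to 0.7, none of which the documents give. The change is worth making because adjustment is nearly free and is preferable to the unadjusted comparison whichever term was meant.

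**What to change.** For MOB versus MOB + MED, replace the unadjusted between-group ANOVA by the difference in final value adjusted for the initial value (ANCOVA), with a 95% confidence interval, for VAS, finger-to-ground distance, RMDQ and ODI. Use the RMDQ and ODI scores, not the category counts. State that the group main effect will not be interpreted. Report the difference in mean change (group-by-time) beside the ANCOVA result, and say that neither estimate should be read as free of confounding unless the randomisation procedure is documented.

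The cost is a change of SAP wording, one degree of freedom, and a re-run on initial values already collected. No new data are needed.

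### The VAS between-group ANOVA is not restricted to patients, so five pain-free controls at VAS 0 appear to enter as a third arm and modestly raise the bar for MOB versus MOB+MED

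*Combined protocol and SAP*

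**What the plan says.** In the combined protocol and SAP, Materials and Methods says that "the volunteers were allocated to three groups":

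- MOB, "consisting of individuals with low back pain and treated with the technique, with a total of 18 participants";
- MOB+MED, people with low back pain "who underwent the mobilization technique associated with medication, a total of 12 participants";
- CONTROL, five people, "constituted by healthy individuals without any kind of injury or pain complaint who received the application of the neural mobilization technique".

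The same section requires a VAS of 4 or more of entering patients and adds: "The subjects in all three groups were submitted to the same evaluation protocol". Its closing statistical paragraph sets a 5% level and a repeated-measures ANOVA "performed to test between-group differences (followed by the Tukey-Kramer post hoc test", with paired t tests within groups. It names no group as excluded from the between-group test. The Results open by counting 35 people as analysed.

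Under Results, Visual Analogue Scale, the MOB mean falls from 8.47 to 4.05. The 30-day values are 1.5 (MOB) and 2.6 (MOB+MED). For CONTROL, "pain intensity on the VAS scale remained at zero until the follow up evaluation". The same subsection reports no significant difference between MOB and MOB+MED and takes this as a sign that mobilization alone can relieve pain.

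**The concern.** CONTROL does not fit the VAS endpoint. Its members differ from patients by the entry rule, receive the same technique, and cannot improve from zero. They therefore say nothing about natural course, regression to the mean or placebo response in people with back pain. The document calls the trial randomized and controlled, so a reader could take a significant VAS group test as evidence of efficacy when it mainly separates people with pain from people without.

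The only VAS comparison between patient groups is MOB versus MOB+MED. Five subjects without variance shrink the pooled error, and two further pairwise comparisons enlarge the Tukey-Kramer critical value. These effects pull in opposite directions, so the net effect has to be calculated. It matters because the text draws a conclusion from the non-significant result.

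**Working it through.** **Inputs.** Group sizes 18, 12 and 5; alpha 0.05 (two-sided assumed); VAS 0-10 with patient entry at 4 or more; CONTROL at 0 throughout; MOB means 8.47 and 4.05; 30-day means 1.5 and 2.6. All are in Materials and Methods or Results of the combined document. No VAS standard deviation is given, so SDs of 1 to 3 are assumed where one is needed. The document states no power or critical value to reproduce. Its analysed total is 18 + 12 + 5 = 35, which includes the controls.

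**1. Baseline group difference.** Put all 30 patients in [4, 10] and the five controls at 0. F is smallest when the two patient arms share a mean m and the patient spread is as large as the range allows:

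- between-group SS = (30 × 5/35) m² = 4.286 m²
- within-group SS ≤ 30 (m − 4)(10 − m)
- F ≥ (4.286 m²/2) ÷ [30 (m − 4)(10 − m)/32] = 2.286 m² ÷ [(m − 4)(10 − m)]

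The minimum is at m = 40/7 = 5.71, giving F = 2.286 × 4.444 = 10.16. The 5% critical value of F(2,32) is 3.29, and p is at most about 0.0004. No patient data allowed by the entry rule can make this test non-significant.

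**2. Other between-group terms.** Simulation used two identical patient arms moving from 8.47 to 4.05, controls at 0, values clipped to 0-10, and 20,000 runs per setting.

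| Term | Assumptions | Significant at 5% |
|---|---|---|
| Group main effect | SD 1-3, correlation 0-0.7 | 100% |
| Group-by-time | SD 1-3, correlation 0.5-0.7 | 92-100% |
| Group-by-time | SD 1-3, correlation 0 | 52-100% |
| 30-day VAS alone, both arms at 1.94 | SD 1-3 | 41-100% |

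The value 1.94 is the weighted mean (18 × 1.5 + 12 × 2.6)/30.

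**3. MOB versus MOB+MED, one-way model with equal patient variances.**

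- Error df: patients 17 + 11 = 28; with CONTROL 28 + 4 = 32.
- CONTROL adds 4 df and no sum of squares, so the pooled variance is 28/32 = 0.875 of the patients-only value. The SE is √0.875 = 0.935 of it, or 6.5% smaller.
- Critical value: patients only, t(0.975; 28) = 2.048. Tukey-Kramer on three groups, q(0.95; 3, 32)/√2 = 2.457, or 20% larger.
- Net bar in patients-only SEs: 2.457 × 0.935 = 2.299. Ratio 2.299/2.048 = 1.122.
- Per-contrast alpha: P(|t₂₈| > 2.299) = 0.029.

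None of these figures depends on the SD.

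**4. Consequence for the 1.1-point gap at 30 days** (2.6 − 1.5). The SE is SD × √(1/18 + 1/12) = 0.373 × SD.

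- Patients only: significant if SD < 1.1/(2.048 × 0.373) = 1.44.
- Three groups: significant if SD < 1.1/(2.299 × 0.373) = 1.28.

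Power for a true 1.1-point difference:

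| Assumed SD | Two groups | Three groups |
|---|---|---|
| 1 | 81% | 74% |
| 1.5 | 48% | 38% |
| 2 | 30% | 22% |
| 2.5 | 21% | 15% |
| 3 | 16% | 11% |

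**The case against.** **Entry of CONTROL is inferred.** The statistical paragraph does not list the groups in the ANOVA, and a count of 35 analysed could include controls who were only described. That stands, and the point is worded accordingly. Still, three groups are defined, the test is unrestricted, Tukey-Kramer is an all-pairs procedure with no purpose for two groups, and nothing in the text contradicts the reading.

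**No reported p-value rests on CONTROL.** This is correct. No omnibus group test or patient-versus-CONTROL p-value is given. The VAS p-values in the Figure 3 legend are within-group comparisons over time, and CONTROL results are already narrated descriptively. A reader might infer that the reported significant VAS improvements are products of the control group; the documents do not support that.

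**The 12% depends on the model.** The plan has repeated measures and many sessions, and defines neither the Tukey-Kramer family nor the error term. Another family or error term would give another figure. That stands as a limit.

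**The effect is small.** The two distortions partly offset, the net effect is conservative, and at an SD of 1.5 or more power for 1.1 points is below 50% either way. That also stands. But a conservative bar is not harmless when the null itself is interpreted. Removing CONTROL would not make non-significance between two mobilized arms into evidence that mobilization works; that weakness in the Results is separate.

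**Disability scores.** A reader might extend the argument to RMDQ and ODI, since all five controls sit in the lowest bands both times. The documents do not support this. There is no disability entry criterion. At baseline, 15 of 17 MOB patients share CONTROL's RMDQ band (Table 2) and 7 of 16 share its ODI band (Table 3). Those bands span 0-10 points and 0-20%, so being in them shows neither a floor nor zero variance. Only category counts are reported.

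**Conclusion.** The concern holds for VAS, with entry of CONTROL as the natural but inferred reading. The baseline group difference is then fixed by eligibility, and the group main effect is significant in practice even with identical patient arms. Neither is evidence of efficacy.

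A reader might infer that every between-group VAS test must come out significant whatever the treatment does. That goes too far: group-by-time and the 30-day comparison are contaminated by the zero controls, but significance there is not certain, particularly with low within-patient correlation or a large SD.

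For MOB versus MOB+MED the bar is about 12% higher and the per-contrast alpha about 0.029 instead of 0.05. This assumes a one-way three-group model, equal patient variances and controls at exactly zero. It modestly favours the null that the Results interpret, but does not show that null to be an artefact: for a 1.1-point gap the result changes only if the patient SD is about 1.28-1.44, and the documents do not give the SD. The change is worth making because it is specific, costs little and affects a stated conclusion.

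**What to change.** In the statistical paragraph of Materials and Methods, state that the VAS between-group analysis compares MOB with MOB+MED only, as a single contrast without Tukey-Kramer across three groups. State that CONTROL is reported descriptively as a healthy reference group and is not an efficacy comparator. Re-run the VAS comparison on that basis and update the MOB versus MOB+MED statement under Results, Visual Analogue Scale, preferably giving the estimated difference, its confidence interval and the SDs.

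The cost is one re-run on existing data and a small text edit. The only loss is an omnibus test that carries no information about efficacy.
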